## SYMPTOMS/SIDE EFFECTS

Please record any side effects experienced during this cycle. Include the date the particular symptom started and when it ended. Please evaluate the severity of the symptom according to the following scale:

**Mild:** Awareness of sign or symptom; easily tolerated and did not affect ability to perform normal daily activities. Symptom did not require medication or therapeutic intervention.

**Moderate:** Significant discomfort which interfered with ability to perform normal daily activities. Symptom was easily resolved with at home medication or simple therapeutic intervention.

**Severe:** Marked discomfort with an inability to carry out normal daily activities. Symptom required new medication and/or therapeutic intervention in order to resolve.

**Please Note:** The severity should reflect the most severe level experienced during the time period.

## 14.4 Prohibited medications

**Prohibited Medications\***

Category	Drug name
Strong inhibitors of CYP3A4/5	Boceprevir, clarithromycin, cobicistat, conivaptan, danoprevir/ritonavir, eltegravir/ritonavir, grapefruit juice, indinavir/ritonavir, itraconazole, ketoconazole, lopinavir/ritonavir, mibefradil, nefazodone, neflifavir, posaconazole, ritonavir, saquinavir, saquinavir/ritonavir, telaprevir, telithromycin, tipranavir/ritonavir, troleandomycin, voriconazole
Strong inducers of CYP3A4/5	Avasimibe, carbamazepine, mitotane, phenobarbital, phenytoin, rifabutin, rifampin (rifampicin) , St. John's wort (hypericum perforatum)
Substrates of CYP3A4/5	Alfentanil, apixaban (doses >2.5 mg only), aprepitant, astemizole, cisapride, cyclosporine, diergotamine, dihydroergotamine, ergotamine, fentanyl, lovastatin, nicardipine, nisoldipine, pimozide, quinidine, rivaroxaban, simvastatin, sirolimus, tacrolimus, terfenadine, thioridazine
Medications with a known risk or possible for QT prolongation and/or Torsades de Pointe (TdP)	Amiodarone, anagrelide, arsenic trioxide, astemizole, azithromycin, bepridil, chloroquine, chlorpromazine, cilostazol, ciprofloxacin, cisapride, citalopram, clarithromycin, disopyramide, dofetilide, domperidone, donepezil, dronedarone, droperidol, erythromycin, escitalopram, flecainide, fluconazole, halofantrine, haloperidol, ibutilide, levofloxacin, levomethadyl, mesoridazine, methadone, moxifloxacin, ondansetron (i.v. only), pentamidine, pimozide, probucol, procainamide, propofol, quinidine, sevoflurane, sotalol, sparfloxacin, sulpiride, terfenadine, thioridazine, vandetanib, venlafaxine
Herbal medications/preparations or dietary supplements that are strong inhibitors or inducers of CYP3A4/5 or those with a known risk of QT prolongation	Herbal preparations/medications are prohibited throughout the study. These herbal medications include, but are not limited to: St. John's wort, Kava, ephedra (ma huang), gingko biloba, dehydroepiandrosterone (DHEA), yohimbe, saw palmetto, black cohosh, and ginseng. Patients should stop using these medications 7 days prior to the first dose of study drug.

\*List applies to formulations of medications that are absorbed systemically

## 14.5 Medications not Recommended

Medications Not Recommended\*

Category	Drug name
Moderate CYP3A4/5 inhibitors	Amprenavir, atazanavir, casopitant, cimetidine, darunavir, diltiazem, fosamprenavir, lomitapide, netupitant, tofisopam, verapamil
Moderate CYP3A4/5 inducers	Bosentan, efavirenz, etravirine, genistein, iversivirine, modafinil, naftcillin, talviraline
Sensitive CYP3A4/5 substrates	Alpha-dihydroergocryptine, almorexant, alpaviroc, apixaban (doses < 2.5 mg only), atazanavir, atorvastatin, avanafil, bosutinib, brecanavir, brotizolam, budesonide, buspirone, capravirine, casopitant, darifenacin, darunavir, ebastine, eletriptan, eplerenone, felodipine, fluticasone, ivacaftor, lomitapide, lumefantrine, lurasidone, maraviroc, midazolam, perospirone, quetiapine, ridaforolimus, sildenafil, ticagrelor, tilidine, tolvaptan, triazolam, vardenafil, vicriviroc, voclosporin
Strong BSEP inhibitors	Bosentan, fusidate, glibenclamide, , sulindac, troglitazone (TGZ-sulfate)
MATE1 and OCT2 substrates	Acyclovir, amantadine, amiloride, cephalexin, cephadrine, cimetidine, famotidine, fexofenadine, memantine, metformin (also a substrate for OCT1, MATE1, and MATE2K), pindolol, procainamide, ranitidine, varenicline
BCRP substrates	Rosuvastatin and sulfasalazine
Medications that carry a possible risk for QT prolongation	Alfuzosin, apomorphine, aripiprazole, atazanavir, atomoxetine, bedaquiline, clozapine, dexmedetomidine, dolasetron, eribulin, famotidine, felbamate, fingolimod, foscarnet, gatifloxacin, gemifloxacin, granisetron, iloperidone, isradipine, lithium, mirabegron, mirtazapine, moexipril, norfloxacin, ofloxacin, olanzapine, ondansetron (p.o. only at 4 mg or 8 mg), oxytocin, paliperidone, pasireotide, pipamperone, promethazine, quetiapine, ranolazine, rilpivirine, risperidone, roxithromycin, sertindole, telavancin, tetrabenazine, tizanidine, tolterodine, vardenafil, ziprasidone

\*List applies to formulations of medications that are absorbed systemically

## 14.6 Adverse event monitoring log (CTCAE 5.0):

Adverse event	Grade 1	Grade 2	Grade 3	Grade 4	Baseline	Mid-cycle visit	End of study
						Mark N/A or grade for each visit AND date of onset	
Rash	<10% BSA	10-30% BSA	Severe rash, >30%, SJS	Any %, requiring antibiotics, TEN			
Interstitial Lung Disease/ Pneumonitis	Asymptomatic	Symptomatic	Severe Symptomatic	Life threatening			
Nausea	Loss of appetite without alteration of eating habits	Oral intake decreased without weight loss, dehydration, malnutrition	Inadequate oral intake, hospitalization indicated	N/A			
Vomiting	Intervention not indicated	Outpatient IV hydration	Tube feeding, TPN, hospitalization	Life threatening			
Diarrhea	Increase of <4 stools per day	Increase of 4-6 stools per day	>7 stools per day over baseline	Life threatening			
Constipation	Occasional or intermittent symptoms; occasional use of stool softeners, laxatives, dietary modification, or enema	Persistent symptoms with regular use of laxatives or enemas	Obstipation with manual evacuation indicated; limiting self-care ADL	Life threatening			
Fatigue	Relived by rest	Not relieved by rest, limiting basic activities of daily living	Limiting self-care	N/A			
Anorexia	Loss of appetite without alteration in eating habits	Oral intake altered without significant weight loss or malnutrition; oral nutritional supplements indicated	Associated with significant weight loss or malnutrition (e.g., inadequate oral caloric and/or fluid intake); tube feeding or TPN indicated	Life-threatening consequences; urgent intervention indicated			

Alopecia	<50% of normal, only obvious to close inspection	>50% of normal, a wig or hair piece is necessary; psychosocial impact	N/A	N/A			
Arthralgia	Mild pain	Moderate pain, limiting activities of daily living	Severe pain, limiting self-care	N/A			
Headache	Mild pain	Moderate pain, limiting activities of daily living	Severe pain, limiting self-care	N/A			
Hot flush *	Mild	Moderate, limiting activities of daily living	Severe	N/A			
Other							
Other							
Other							

Abbreviations: LLN: lower limit of normal; ULN: upper limit of normal; BSA: body surface area

\*No CTCAE

Baseline visit → Completed by \_\_\_\_\_ Date: \_\_\_\_\_  
 Mid-cycle 1 visit → Completed by \_\_\_\_\_ Date: \_\_\_\_\_  
 End of study visit → Completed by \_\_\_\_\_ Date: \_\_\_\_\_

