Grade 1 (< 10% body surface area (BSA) with active skin toxicity, no signs of systemic involvement)	Grade 2 (10-30% BSA with active skin toxicity, no signs of systemic involvement)	Grade 3 (severe rash not responsive to medical management; > 30% BSA with active skin toxicity, signs of systemic involvement present; SJS*)	Grade 4 (any % BSA associated with extensive superinfection, with IV antibiotics indicated; life threatening consequences; TEN**) )
No dose adjustment is required.  Initiate appropriate medical therapy and monitor as clinically indicated.		Interrupt ribociclib until the etiology of the reaction has been determined.  If the etiology is a SCAR, permanently discontinue ribociclib. If the etiology is not a SCAR, interrupt dose until recovery to Grade $\leq$ 1, then resume ribociclib at the same dose level. If the cutaneous adverse reaction still recurs at Grade 3, resume ribociclib at the next lower dose level.	Permanently discontinue ribociclib.

Abbreviations: Severe Cutaneous Adverse Reactions (SCARs); Stevens-Johnson Syndrome (SJS); Toxic Epidermal Necrolysis (TEN)
 
* SJS (Grade 3 and 4) is defined as skin sloughing covering <10% BSA and 10-30% BSA, respectively, with associated signs (e.g., erythema, purpura, epidermal detachment and mucous membrane detachment)
 
** TEN (Grade 4) is defined as skin sloughing covering <math>\geq</math>30% BSA with associated symptoms (e.g., erythema, purpura, epidermal detachment, and mucous membrane detachment).
			

Table 7: Dose Modification and Management for QT Prolongation

ECGs with QTcF* > 480 ms	
 
Interrupt ribociclib treatment ms
 
If QTcF prolongation resolves to < 481 ms, resume treatment at the next lower dose
 
If QTcF <math>\geq</math> 481 ms recurs, interrupt dose until QTcF resolves to < 481 ms; then resume ribociclib at next lower dose level.
 

ECGs with QTcF* > 500 ms	
 
Interrupt ribociclib treatment if QTcF greater than 500 ms
 
If QTcF prolongation resolves to < 481 ms, resume treatment at the next lower dose level.
 
 
Permanently discontinue ribociclib if QTcF interval prolongation is either greater than 500 ms or greater than 60 ms change from baseline AND associated with any of the following: Torsades de Pointes, polymorphic ventricular tachycardia, unexplained syncope, or signs/symptoms of serious arrhythmia.

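### The rash Grade 4 cell of the 14.6 adverse event log does not match Table 6: it is looser on antibiotics and omits life-threatening rash

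*Combined protocol and SAP*

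**What the plan says.** Section 4.3.10 has each adverse event's grade, based on CTCAE 5.0, and its start date documented on the monitoring form in Appendix 14.6. The form is headed CTCAE 5.0, prints criteria for each grade, and asks for a grade or N/A at baseline, mid-cycle and end of study. For rash, Grades 1 and 2 are set by body surface area (BSA) alone. The Grade 4 cell reads "Any %, requiring antibiotics, TEN".

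Section 5.4 also grades by CTCAE 5.0. In its Table 6:

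- Grade 1 is a rash on less than "10% body surface area (BSA) with active skin toxicity, no signs of systemic involvement".
- Grade 2 is "10-30% BSA with active skin toxicity, no signs of systemic involvement".
- For both of these the action is "No dose adjustment is required", followed by "Initiate appropriate medical therapy and monitor as clinically indicated".
- Grade 4 is "any % BSA associated with extensive superinfection, with IV antibiotics indicated; life threatening consequences; TEN", and the action is to "permanently discontinue ribociclib".

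**The concern.** The log and Table 6 claim the same grading system, yet their Grade 4 definitions for rash differ in substance. An assessor who follows the printed cell can record Grade 4 because an antibiotic was needed, whatever its route and however limited the rash.

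Two things are at stake. One is the accuracy of the rash grade in the safety record of a study that compares toxicity between race-based cohorts as a secondary objective. The other is that a Grade 4 entry might be carried over to Table 6, where that grade ends ribociclib permanently. Rash is a row likely to be used, since Table 3 lists it among the events seen in more than 20% of patients in one of the pivotal trials.

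**Working it through.** There is no sample size, power or event figure to reproduce. The check is a comparison of the two texts.

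| Grade | Log 14.6, rash row | Table 6, definition and action |
|---|---|---|
| 1 | BSA under 10% | BSA under 10%, no systemic signs; treat, dose unchanged |
| 2 | BSA 10 to 30% | BSA 10 to 30%, no systemic signs; treat, dose unchanged |
| 3 | Severe rash, BSA over 30%, or SJS | Severe and unresponsive to treatment, BSA over 30%, systemic signs, or SJS; interrupt, then stop if a SCAR |
| 4 | "Any %, requiring antibiotics, TEN" | "any % BSA associated with extensive superinfection, with IV antibiotics indicated; life threatening consequences; TEN"; permanent stop |

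**What the log omits.** Three elements of Table 6's Grade 4 are missing: extensive superinfection, the intravenous route, and life-threatening consequences.

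**Whether the log's terms must all be met together.** They cannot be. The Table 6 footnote defines TEN as sloughing of at least 30% BSA, which is incompatible with a rash of any extent. TEN and the need for antibiotics are therefore alternatives, and antibiotic use is a route to Grade 4 by itself.

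**Case A: 5% BSA, no systemic signs, responsive to treatment, oral or topical antibiotic.** The log's Grade 4 cell is met, and so is its Grade 1 cell. Table 6 gives Grade 1. If the higher cell is marked, the difference is 4 − 1 = 3 grades.

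**Case B: the same rash on 20% BSA.** The log's Grade 4 and Grade 2 cells are both met. Table 6 gives Grade 2. The difference is 4 − 2 = 2 grades.

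In both cases Table 6 calls for treatment without a dose change, so needing an antibiotic cannot by itself mark Grade 4 there.

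**Case C: life-threatening rash, no antibiotics required, no TEN.** Table 6 gives Grade 4. The log has no Grade 4 criterion that applies, so the highest available grade is 3, a difference of at least 4 − 3 = 1.

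**Secondary: SJS with sloughing on 10 to 30% BSA.** The log lists SJS only at Grade 3, as does the Grade 3 column of Table 6, but the Table 6 footnote puts this extent at Grade 4. The difference is 4 − 3 = 1 in the recorded grade. Dosing is unaffected, because Table 6 already says "If the etiology is a SCAR, permanently discontinue ribociclib".

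**Whether this is only abbreviation.** Of the 12 named log rows, two have their own section 5.4 table: rash (Table 6) and pneumonitis (Table 5). The pneumonitis row is equally short and agrees with Table 5. Six rows define a Grade 4. Five of them (pneumonitis, vomiting, diarrhea, constipation, anorexia) use a life-threatening criterion; rash is the only one that does not.

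**The case against.** The strongest reply is that the log is a one-page summary. Sections 4.3.10, 5.4 and 8.7 all point the investigator to CTCAE 5.0, the cell places antibiotics beside TEN, and almost every other Grade 4 cell says life-threatening. An experienced assessor would be unlikely to give a small rash on a topical antibiotic a Grade 4. This has force: it lowers the chance of misgrading. It does not correct the cell, since the form presents its printed criteria as CTCAE 5.0 and no rule says that Table 6 overrides it.

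Three stronger readings are tempting, and the documents do not support them.

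- **That the log makes such a rash Grade 4.** It only permits this. The rash also fits the log's Grade 1 or 2 cell, and nothing says the higher cell wins.
- **That the form directs patients off ribociclib.** The log carries no dose action. The rash discontinuation rule is in Table 6, printed with the full Grade 4 definition, so anyone looking up the action sees the correct criteria.
- **That the toxicity analyses are compromised.** Section 9.2 names no analysis by rash grade. It describes adverse events, models whether particular events occur, and tabulates patient-reported frequencies; a wrong grade changes neither occurrence nor frequency. Its one grade-based regression concerns neutropenia, which is not a log row. The patient-reported rash item is yes or no, and rash is not a secondary endpoint in section 2.4. A table by grade under section 9.4 is possible but not specified.

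**Conclusion.** The inconsistency is real and the log cell should be corrected. It is at the lowest end of minor. One row of an operative safety form carries a Grade 4 threshold that is too low for antibiotic use and has no place for a life-threatening rash outside its two listed routes. The recorded grade can be 2 or 3 too high in the first situation and at least 1 too low in the second. There is also a small risk of an unneeded permanent discontinuation. The AUC comparison, the sample size, the endpoints, the named analyses and the dosing rules stand as they are.

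The Grade 1 or 2 result assumes no systemic involvement and a rash that responds to treatment; otherwise Table 6 may give Grade 3. Confidence is high that the wording differs, and lower that misgrading would follow in practice. The documents give no rate of antibiotic-treated rash in cycle 1, so no number of affected patients can be stated.

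**What to change.** - Replace the rash Grade 4 cell in 14.6 with Table 6's wording: "any % BSA associated with extensive superinfection, with IV antibiotics indicated; life threatening consequences; TEN".
- Optionally, split SJS between Grades 3 and 4 by BSA, as the Table 6 footnote does.
- Add one sentence to 4.3.10 stating that the section 5.4 definitions govern any grade used for a dose decision.
- Recheck rash entries already logged as Grade 4 against Table 6.

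The cost is one form cell, one sentence and a short notice to sites. The recheck can be confined to existing Grade 4 rash entries. Life-threatening rashes, the converse error, should already be traceable as serious adverse events under section 8.5.
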